10 SAFETY ASSESSMENTS

All AEs observed by study subjects, investigators or other study staff from informed consent through last study follow up visit will be recorded. If a SAE or unanticipated serious device related effect (USADE) occurs, study subjects may be requested to appear for unscheduled follow up visits for AE assessment and hand photographs.

The following information, at minimum, must be recorded:

- AE description
- AE type (serious, expected, unexpected) Refer to definitions below
- Start and Stop Dates
- Intensity (mild, moderate, severe) Refer to definitions below
- Causal relationship (not related, related) Refer to definitions below
- Treatment description, if any

10.1 Definition of intensity

The clinical intensity of an AE will be classified as:

Mild: Signs and symptoms that can be easily tolerated. Symptoms can be ignored and disappear when the subject is distracted.

Moderate: Signs and symptoms that cause discomfort and interfere with normal functioning, but are tolerable. They cannot be ignored and do not disappear when the subject is distracted.

Severe: Signs and symptoms that affect usual daily activity and incapacitate the subject, thereby interrupting his/her daily activities.

The definitions above are difficult to apply for some data (e.g., clinically relevant laboratory values that are documented and evaluated on the CRF AE report form). In such situations, the investigator should make a judgment based on personal experience.

10.2 Definition of causal relationship

An AE is considered to be "related" to investigational product (IP) if a causal relationship between the IP and an AE is at least a reasonable possibility (i.e., the relationship cannot be ruled out) in the opinion of the investigator.

The expression "reasonable causal relationship" is meant to convey that there are facts (evidence) or arguments to suggest a causal relationship (ICH E2A guideline). Otherwise, the relationship should be considered as "not related."

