5.2 Endpoints

The primary safety endpoint of the study is the 6-month rate of device/injection-related severe adverse events

The secondary endpoints of the study are:

- The rate of device/injection-related severe adverse events at 24 months
- MHGS at 3-months after initial treatment
- MHGS at 3-months following retreatment for those receiving retreatment
- GAIS at 3-months after initial treatment
- GAIS at 3-months following retreatment for those receiving retreatment
- Hand function testing at baseline, study exit, and other collected time points
 - Inter-rater correlation of hand function testing results for each site
 - Differences between sites in hand function testing results

Figure 1. Merz Hand Grading Scale (MHGS).

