7.1. Primary Safety Endpoint

The primary safety endpoint analysis will be based on a non-inferiority hypothesis test. Stated in terms of the null and alternate hypothesis, this is as follows:

Ho (null):  $P_A - P_B \ge 12\%$  vs

Ha (alternate): PA – PB < 12%

Where PA and PB are the percentages of subjects in Groups A and B who experience a device/injection-related severe adverse event by 6 months. Percentages will be calculated using the number of subjects experiencing at least one device/injection related severe treatment emergent adverse event (TEAE) by six months posttreatment as the numerator divided by the number of subjects in the SES (PPS) population with six month follow-up data.

TEAEs are defined as adverse events with onset or worsening after the first injection of Radiesse.

The test will be based on the Farrington-Manning likelihood score test. Testing will be done by constructing a one-sided 95% confidence interval using the Farrington-Manning method. If the upper 95% confidence bound around  $P_A - P_B$  is less than 12%, Ho will be rejected in favor of Ha, thus demonstrating non-inferiority, otherwise the Ho will be accepted.

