### 7.4. Additional Safety Analyses

The number and percentage of subjects experiencing physician reported TEAEs as well as the number of events itself will be reported for the following time periods:

- following initial treatment but occurring before retreatment,
- following month 6 retreatment but occurring before further retreatment,

- following month 12 retreatment but occurring before further retreatment,
- following month 18 retreatment but occurring before further retreatment.

The same will be done for subject-reported TEAEs.

Further, both, physician- and subject-reported TEAEs, will be analysed by maximum severity, by maximum duration and by number of treatments. Physician-reported TEAEs will additionally be analysed by maximum relationship.

In case of missing diary entries, the duration of a subject-reported TEAE will be calculated as follows:

- a. If the subject misses ONE day of diary entry, it is assumed that they had the event during that day they "forgot". The event will be counted as one TEAE then.
  - *i.* Example= Bruising reported on days 1, 2, 4, 5 and no diary entry on day 3; this would be a 5 day bruise of one TEAE
  - *ii.* Example= Swelling reported on days 2, 4, 5, 7 and no diary entry on day 3 or 6; this would be a 6 day swelling of one TEAE
- b. If the subject misses TWO OR MORE days of diary entry, it is assumed that they did NOT have the event during the 2 days they "forgot," and two unique TEAEs will be counted.
  - *i.* Example= Swelling reported on days 2, 3, 6, 7, 8 and no diary entry on days 4 and 5; this would be one TEAE of swelling lasting 2 days and one TEAE of swelling lasting 3 days (two unique subject-reported TEAEs)
  - *ii.* Example= Redness reported on days 1, 2, 3, 4, 7,8 and no diary entry on days 5 and 6; this would be one TEAE of redness lasting 4 days and one TEAE of redness lasting 2 days (two unique subject-reported TEAEs)

Differences between percentages of subjects with physician reported TEAEs in groups A and B will be presented together with exploratory 95% confidence intervals. The same will be done for subject-reported adverse events.

In addition, the number and percentage of subjects experiencing serious physician reported TEAEs as well as the number of events itself will be reported.

Kaplan-Meier time to event analyses will be performed for physician-reported adverse events.

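### Relatedness is defined only against the investigational product, but the primary endpoint counts device- or injection-related severe AEs, so qualifying events can be coded out of the primary numerator

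*Protocol*

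**What the plan says.** Protocol 5.2 sets the endpoint: "The primary safety endpoint of the study is the 6-month rate of device/injection-related severe adverse events". Protocol 12.4.1 and SAP 7.1 carry the same device/injection attribution into the hypothesis test. Neither document defines injection-related.

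Causality is one of the items that Protocol section 10 requires for each AE: "Causal relationship (not related, related) Refer to definitions below". The definition referred to is in Protocol 10.2. An event is related "if a causal relationship between the IP and an AE is at least a reasonable possibility", which 10.2 explains as meaning that "the relationship cannot be ruled out". The remainder is assigned by default: "Otherwise, the relationship should be considered as" not related. The injection procedure and the lidocaine are not mentioned there.

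Protocol 8.1.1 describes the product as the Radiesse implant, calcium hydroxylapatite in a gel carrier. Under 8.2.2, lidocaine is mixed in before injection and is not supplied by the sponsor. Protocol 4.3 lists the lidocaine risks separately from those of injecting Radiesse.

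On sources of events, Protocol section 10 says: "All AEs observed by study subjects, investigators or other study staff from informed consent through last study follow up visit will be recorded". SAP 7.4 reports physician-reported and subject-reported TEAEs as two streams, both by severity, and then adds: "Physician-reported TEAEs will additionally be analysed by maximum relationship". SAP 7.1 does not say which stream, or whether both, supplies the primary numerator.

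**The concern.** The endpoint has two qualifying attributions and the coding rule has one. An investigator who judges that a severe event came from needle trauma, the injection procedure or the anesthetic, and not from the implant, is told by 10.2 to code it as not related. The same event meets the endpoint as worded.

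The protocol itself treats injection as a separate attribution. Sections 6.1 and 9.2 and the footnotes to Table 2 call for Week 2 photographs when a severe AE is related to the device and/or the injection. The causality rule was not written to match.

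The second gap concerns diary events. If only one stream carries a relationship analysis and SAP 7.1 is silent on source, two analysts could build different primary numerators from the same data.

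This matters because the test uses a fixed margin of 12 percentage points. If events are lost in proportion to each group's rate, the observed difference shrinks while the margin does not, and a true excess at the margin passes more often. The physicians who assess AEs are not blinded (SAP 4.2), so coding could also differ by group.

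**Working it through.** **Inputs.** From Protocol 12.1 and SAP 3: expected rate 17% in both groups, margin 12 points on P_A − P_B, Farrington-Manning score test, one-sided alpha 0.05, 122 per group, power about 80%. The fraction of qualifying events lost is an assumption, since the documents give none.

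**Step 1: reproduce the plan's figure.**

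- Unpooled formula: n = (1.645 + 0.842)² × 2 × 0.17 × 0.83 / 0.12² ≈ 121.2, rounded up to 122 per group. Power at 122 is 80.2%.
- Farrington-Manning, asymptotic: the constrained rates under a difference of 0.12 are 0.2454 and 0.1254. This gives SE₀ = √[(0.2454 × 0.7546 + 0.1254 × 0.8746)/122] = 0.0492 and SE₁ = √(2 × 0.17 × 0.83/122) = 0.0481. Power = Φ[(0.12 − 1.645 × 0.0492)/0.0481] = 79.2%.
- Farrington-Manning, exact binomial enumeration: 79.7%.

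The stated 80% is reproduced.

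**Step 2: false non-inferiority at the margin with all events counted.** True rates are 17% + 12 points = 29% in Group A and 17% in Group B. The exact probability of declaring non-inferiority is 5.0%.

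**Step 3: the same fraction f lost in both groups.** Observed rates are 29% × (1 − f) and 17% × (1 − f). The last column starts from true rates of 17% in both groups.

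| f | Observed A vs B | Observed difference | False non-inferiority | Chance of passing, true rates equal |
|---|---|---|---|---|
| 0 | 29.0% vs 17.0% | 12.0 | 5.0% | 79.7% |
| 5% | 27.55% vs 16.15% | 11.4 | 6.3% | 81.1% |
| 10% | 26.1% vs 15.3% | 10.8 | 7.9% | 82.4% |
| 20% | 23.2% vs 13.6% | 9.6 | 12.3% | 85.2% |

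**Step 4: the same number of points lost in both groups.** The observed difference stays at 12 points.

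| Points lost | Observed A vs B | False non-inferiority | Chance of passing, true rates equal |
|---|---|---|---|
| 2 | 27% vs 15% | 5.0% | 82.9% |
| 5 | 24% vs 12% | 5.0% | 88.0% |
| 8 | 21% vs 9% | 4.9% | 93.3% |

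**Step 5: loss in one group only.** For 10% and 20% lost, false non-inferiority is 13.8% and 30.4% if the loss is in Group A, and 2.5% and 1.1% if it is in Group B.

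The definitional gap is fixed by the text, but its effect on the test depends on the pattern of loss, which the documents do not determine.

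**The case against.** The strongest reply is that few events would be lost. Under 10.2 an event is related whenever a link to the product cannot be excluded. The lidocaine is mixed into the Radiesse syringe and delivered through the same needle, so for a severe local hand event the product can seldom be excluded. Protocol 4.3 treats bruising, swelling and redness as risks of injecting Radiesse and regards lidocaine side effects as unlikely at the doses used. The Week 2 photograph rule shows that sites must already recognise injection-related severe events. The list in section 10 is a stated minimum, and the CRF, which is not among the documents, may hold a separate injection item. All of this stands, and it limits the likely size. It does not remove the mismatch: 10.2 is the only written rule, and neither document links it to the endpoint.

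Three stronger readings are tempting and are not supported.

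- **A reader might infer that the definition necessarily favours non-inferiority.** Steps 4 and 5 show otherwise. Error at the margin rises when loss is proportional to the rates or greater in Group A. It stays near 5% when the absolute loss is equal and falls when only Group B loses events. Protocol section 7 expects that Group A may receive higher volumes, which makes greater loss there conceivable. But more volume also means more product, and so more events that 10.2 would code as related.
- **A reader might infer that severe diary events have no route into the numerator.** Section 10 requires intensity and causality for AEs that subjects observe, diaries are collected at visits where a physician assesses AEs, and SAP 7.1 does not restrict the source. SAP 7.4 covers additional analyses and does not govern 7.1. The fair statement is that the source is unspecified.
- **A reader might picture very large losses.** Half of all qualifying events would give 41.1% false non-inferiority, but nothing in the documents supports such a loss under this threshold.

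**Conclusion.** The concern holds as a mismatch between the causality rule and the primary endpoint, together with an unspecified event source in SAP 7.1. Following 10.2 literally can drop events that the endpoint counts. This should be corrected, because it defines the primary numerator and the same attribution recurs in the 24-month rate (SAP 7.2) and in the whole-study rate and Kaplan-Meier analysis (SAP 7.4).

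The number of events lost is unknown and probably small. The rise in false non-inferiority from 5.0% to 6.3–12.3% is an illustration. It assumes true rates of 29% and 17%, 122 evaluable subjects per group, and 5–20% of qualifying events lost in the same proportion in both groups. With an equal absolute loss, the only consequence is that passing becomes easier when the true rates are equal; error at the margin is preserved. Loss confined to Group B is conservative. No direction of bias can be asserted from the documents alone.

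**What to change.** 1. **Protocol 10.2:** define an AE as related if the device, the injection procedure or the mixed lidocaine is at least a reasonable possibility as its cause.
2. **SAP 7.1:** state that either attribution, device or injection, qualifies for the numerator. State also that severe events from both physician reports and subject diaries count, using the investigator-assigned relatedness that Protocol section 10 already requires. Carry the same wording to SAP 7.2 and 7.4.
3. **Sensitivity analysis:** repeat the primary comparison counting every severe AE with onset within 30 days of injection as related, whatever its code. The window matches the diary period and shows whether the conclusion depends on coding.

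SAP version 2.0 is dated February 2019 and refers to some data as not having been collected, so AE coding may be well advanced. If so, items 2 and 3 can still be done without asking unblinded physicians to re-attribute past events, which would carry its own risk of bias.

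The cost is a short protocol change, a few lines in the SAP and one extra table. Sample size does not change. The reported severe AE rate may be slightly higher.

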10.3 Definition of type

10.3.1 Adverse event

The general definition for an AE is an untoward medical occurrence which does not necessarily have a causal relationship to the investigational product.

10.3.2 Serious adverse event

A SAE is an AE that meets at least 1 of the following 6 criteria:

- (1) Results in death.
- (2) Is life-threatening.⁵
- (3) Requires inpatient hospitalization, or prolongation of existing hospitalization.
- (4) Results in persistent or significant incapacity or substantial disruption of the ability to conduct normal life functions.
- (5) Is a congenital anomaly/birth defect.
- (6) Is an important medical event⁶, including an event that requires medical or surgical intervention necessary to preclude permanent impairment of a body function or permanent damage to a body structure.

All SAEs that occur during the study period, whether considered to be related to the IP or not must be reported by e-[contact]) or e-mail sent within 24 hours of knowledge of the event.

Please send completed SAE forms to: [contact] Product Safety Department Merz North America, Inc. [name]

⁵ Defined as the subject being at risk of death at the time of the event; it does not refer to an event that hypothetically might have caused death if it were more severe.

⁶ According to ICH E2A, CPMP/ICH/377/95: "Medical and scientific judgment should be exercised in deciding whether expedited reporting is appropriate in other situations, such as important medical events that may not be immediately life-threatening or result in death or hospitalization but may jeopardize the patient/subject or may require intervention to prevent one of the other outcomes listed in the definition above. These should also usually be considered serious. Examples of such events are intensive treatment in an emergency room or at home for allergic bronchospasm; blood dyscrasias or convulsions that do not result in hospitalization; or development of drug dependency or drug abuse."

Although all information required for completion of an SAE report form may not be available within the specified time period, the following minimal initial information should be reported: Subject ID #, Site #, name and contact information (of investigator/study coordinator), and which of the 6 SAE criteria identified above resulted in the event being deemed "serious".

IRB reporting requirements may also apply for SAEs.

10.3.3 Unanticipated adverse device effect

An unanticipated adverse device effect is any serious adverse effect on health or safety or any life-threatening problem or death caused by, or associated with, a device, if that effect, problem, or death was not previously identified in nature, severity, or degree of incidence in the IFU or Radiesse labeling, or any other unanticipated serious problem associated with a device that relates to the rights, safety, or welfare of subjects.

10.3.4 Expected adverse events

An expected AE is an experience listed in the current IFU (Appendix A).

10.3.5 Unexpected adverse events

An unexpected AE is an experience not previously reported in nature, severity, or incidence in the current IFU. IRB reporting requirements may also apply.

11 QUALITY CONTROL AND QUALITY ASSURANCE

11.1 Monitoring

This study will be monitored in accordance with GCP and regulatory guidelines. By signing this protocol, the investigator agrees to periodic, on-site monitoring of all appropriate study documentation. The progress of the study will be monitored by periodic on-site visits and frequent communications between the Sponsor (or designee) and the investigator (either by phone, fax, email, or post). During these contacts, the monitor will:

- Check and assess the progress of the study.
- Conduct source document verification to ensure data are authentic, accurate, and complete.
- Identify any issues and address their resolution.
- Ensure the safety and rights of subjects are being protected.
- Verify that the study is being conducted in accordance with the currently approved protocol (and any amendments) per GCP and all applicable regulatory requirements.

In addition, the monitor will check whether all AEs and SAEs have been reported appropriately within the time periods required.

The investigator and all staff will be expected to cooperate with the monitor by providing any missing information whenever possible. The investigator must be available to answer questions arising during regular monitoring visits.

11.2 Audits / Inspections

Audits may be performed, including the possibility that a member of the sponsor's quality assurance function or their representative may arrange to visit the investigator in order to audit the performance of the study at the study site, as well as all study documents originating there.

Inspections by regulatory authority representatives and IRBs are possible at any time, even after the end of study. The investigator is to notify the Sponsor immediately of any such inspection. The investigator and institution will permit study-related monitoring, audits, reviews by the IRB and/or regulatory authorities, and will allow direct access to source data and source documents for such monitoring, audits, and reviews.

12 STATISTICAL METHODS

This section describes the statistical analyses foreseen at the time of study planning.

Any deviations from planned analyses, the reasons for such deviation, and all alternative or additional statistical analyses that may be performed before database close will be summarized in the clinical study report.

12.1 Determination of sample size

The primary endpoint will be based on a non-inferiority hypothesis test comparing the 6month rate of device/injection-related severe AEs in the MHGS4 (Group A) subjects versus the MHGS2-3 (Group B) subjects. Based on the pre-market study data, an expected rate of severe adverse events is 17% for both groups, and the test will be based on a 12% non-inferiority margin. This margin allows for adequate power of the planned hypothesis test with a reasonable sample size and will provide assurance that the severe AE rate in the MHGS4 subjects is not unacceptably higher given the expected benefit in these subjects. The test will be based on a one-sided Farrington-Manning likelihood score test of binomial proportions at a one-sided 0.05 alpha level. A maximum of 250 subjects with MHGS grades 2, 3 and 4 at baseline (at least 50% with both hands rated MHGS 4) will be enrolled in at least 5 sites and a maximum of 12 sites in the US. Allowing for some attrition, a total of 244 subjects (122 in each group) at 6 months will provide approximately 80% power to conduct the hypothesis test. Based on an expected attrition rate of 5% per year, a minimum of 225 evaluable subjects are required to provide 2-year follow-up data. Safety and effectiveness data that are collected after 6 months and up to 2 years will be presented descriptively.

12.2 Analysis sets

The safety and per protocol analysis sets will be used for analysis of the study. Differences in results between analysis sets will be explored.

12.2.1 Safety Evaluation Set (SES)

The SES is the subset of all subjects who were exposed to the study device at enrollment. This will be the basis of the primary analysis of the primary safety endpoint.

12.2.2 Per Protocol Set (PPS)

The PPS is the subset of subjects in the SES without major protocol deviations. Examples of a major protocol deviation would be absence of Radiesse hand treatment or receiving an exclusionary hand procedure during the study.

12.3 Variables for analysis

12.3.1 Primary safety variable

The primary safety variable is evaluation of 6-month rate of device/injection-related severe AEs in MHGS4 (Group A) subjects versus MHGS2-3 (Group B) subjects.

12.4 Statistical analysis methods

12.4.1 Primary safety variable

The primary endpoint analysis will be based on a non-inferiority hypothesis test. Stated as a null and alternative hypothesis test:

Ho: $P_A - P_B \ge 12\%$

Ha: $P_A - P_B < 12\%$

Where P_A and P_B are the percentages of subjects in Groups A and B who experience a device/injection-related severe adverse event by 6 months. The test will be based on the Farrington-Manning likelihood score test and a one-sided 0.05 alpha level.

12.4.2 Secondary

and safety variables

The numbers and percentages of subjects experiencing events will be reported by visit. Descriptive statistics will be provided for all study endpoints. Corresponding 95% confidence intervals will be calculated as appropriate.

Events of interest include AEs, as well as efficacy outcomes, including GAIS results (i.e. any improvement vs. no improvement), and an improvement by at least 1 point on the MHGS in both hands, and hand function tests, in particular incidence of a significant MHQ change⁷ or report(s) of severe difficulty performing activities with the hand(s) or severe loss of sensation in the hand(s) since previous visit. The definition of a significant MHQ change are defined for this study as score changes of 11 for pain and 13 for function domain. These values are equivalent to the published data for rheumatoid arthritis patients.

Incidence of AEs over time will be analyzed via Kaplan-Meier time to event analyses. Event duration, severity, and incidence of recurrence will be analyzed. A particular focus will be the time to event for any AE not previously observed in the pre-market study.

Repeated measures models for the percentage of subjects experiencing events over time may be explored to characterize time trends. These will be based on logistic regression models fit via generalized estimating equations with a repeated term for subjects to account for correlation. Repeated measures models may also be employed for continuous measures, again with repeated terms for subjects to account for correlation.

Subgroup analyses will be performed for the primary efficacy and safety endpoints. Outcomes by MHGS group (A versus B) will be analyzed further by age (<60 years versus \geq 60 years) by Fitzpatrick skin type (Grades I, II, and III versus Grades IV, V, or

⁷ Shauver et al, "The Minimal Clinically Important Difference of the Michigan Hand Outcomes Questionnaire," Journal of Hand Surgery, March 2009, 34A:509-514.

SOP/245/EN - CLINICAL STUDY PROTOCOL Page 41 of 48 Merz North America, Inc. Confidential and Proprietary Information. Do not disclose without authorization.

VI), by initial and repeat injection volumes, and by study site by injection volume. In these analyses, subjects will be dichotomized based on injection volume less than or greater than or equal to the median injection volume. This will be done by hand (initial total injection volume per hand) and by subject (initial total injection volume by subject). Injection volumes will be recorded separately for the right hand and the left hand of each subject in the CRF for each treatment administered.

Subgroup analyses will be based on logistic regression models for the primary endpoints as a function of the subgroups, and with the appropriate interaction term. For example, for models comparing the MHGS groups by subgroup, model terms will include the MHGS group, subgroup term, and a term for the interaction of MHGS group and subgroup. Similarly, for the analysis of study site by injection volume, model terms will include MHGS group, study site, dichotomized injection volume, and the corresponding two and three way interaction terms. Analyses by hand will be based on generalized estimating equation models to account for correlations. A p-value of less than 0.05 for the appropriate interaction term will be considered statistically significant. Any such finding will result in additional exploratory analyses to understand possible causes and the clinical significance

Data from the baseline MHGS4 and baseline MHGS2-3 groups will be analyzed separately and in aggregate via descriptive statistics in addition to the above hypothesis test, with appropriate treatment of the follow-up time of each group.

Frequency tables (counts and percentages) and their confidence intervals (based on the binomial distribution) will be presented.

Hand function data will be summarized descriptively and compared to baseline. Hand function data will be evaluated in relation to

eport(s) of severe difficulty performing activities with the hand(s) or severe loss of sensation in the hand(s) since previous visit. Correlation will be plotted between 2 hand function test investigators for the first 10 subjects enrolled at each site. Differences between sites in hand function results will be summarized descriptively and compared to baseline.

